5. STUDY DESIGN

This is a Phase II multicenter, prospective, single arm study. Target inclusion for this study is 226 tumors. It is estimated this study will enroll 150 patients across approximately 15 study sites in the United States and internationally in order to achieve the target tumor goal. Patients enrolled will undergo cryoablation of at least 1 metastatic pulmonary tumor via a Galil Medical cryoablation system using Galil Medical cryoablation needles.

Patients will be screened before the cryoablation procedure. After the cryoablation procedure, protocol directed follow-up visits will occur within 1 week of the cryoablation procedure and then 1, 3, 6, 12, 18, and 24 months post cryoablation procedure.

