Galil Medical**CUC13-LNG079-02: Multi-center Study of Metastatic Lung Tumors Targeted by Interventional Cryoablation Evaluation (SOLSTICE)****Statistical Analysis Plan (SAP)****Table of Contents**

Protocol Summary	2
Objective	2
Study Design.....	2
Sample Size Justification.....	2
General Analysis Methods	3
Analysis Populations	3
Efficacy Endpoint Analysis	4
Efficacy Endpoint.....	4
Analysis Methods	4
Safety Endpoint Analysis.....	4
Safety Endpoint	4
Analysis Methods	4
Supportive Endpoint Analyses	5
Tumor control (patient level & weighted average response).....	5
Tumor control (pulmonary metastatic disease).....	5
Tumor control (additional cryoablation).....	5
Technically successful treatment	5
Disease recurrence or progression	5
Intra-procedural data	6
Physical performance and quality of life.....	6
Additional Data Summaries	7
Subject Disposition.....	7
Randomization and Blinding	8
Handling of Missing Data	8
Subset Analyses	8
Poolability Analyses	8
Interim Reporting.....	9
Statistical Software	9
Version, Revision History, and Approvals	10

Current Version	10
Revision History.....	10
Approvals.....	11

Protocol Summary

Objective

The objective of this study is to assess the safety and to demonstrate efficacy of cryoablation in local tumor control for tumors ≤ 3.5 cm in patients with pulmonary metastatic disease.

Study Design

This is a Phase II multicenter, prospective, single arm. Target inclusion for this study is 226 lesions. It is estimated this study will enroll 150 patients in order to achieve the target lesion goal. Patients enrolled will undergo cryoablation of at least 1 metastatic pulmonary tumor via a Galil Medical cryoablation system using Galil Medical cryoablation needles.

Patients will be screened within 8 weeks of the cryoablation procedure. After the cryoablation procedure visit date, protocol directed follow-up visits will consist of within 1 Week of the cryoablation procedure and then 1, 3, 6, 12, 18, and 24 months post cryoablation procedure.

Sample Size Justification

This is a prospective, single-arm study designed to determine the safety and efficacy of Galil Medical's Cryoablation System and needles in cryoablation of metastatic lung tumors.

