The primary efficacy endpoint for the trial is 12-month local control. The papers shown below were used as reference for clinicians who determined a clinically relevant efficacy endpoint performance goal was 84% success at 12-months. This observed cryoablation group's local control rate will be tested against this performance goal.

Paper	Lesions	12-month Local Control Success	Lower 97.5% 1-sided Wilson CI
Okuneiff (2006)	125	91%	0.8469
Rusthoven (2009)	63	100%	0.9425
Baschnagel (2013)	47	97%	0.8757
Ricardi (2012)	77	94%	0.8632
Norihisa (2008)	43	94.50%	0.8337
Yoon (2006)	101	90%	0.8261

This test is accomplished by testing against the following hypotheses:

$$H_0: C_{\text{DEVICE}} \leq 84.0\%$$

$$H_a: C_{\text{DEVICE}} > 84.0\%$$

where C_{DEVICE} is the observed cryoablation local control rate at 12-months.

The null hypothesis will be rejected and the primary efficacy endpoint performance goal will be met if the lower bound of the one-sided 97.5% confidence interval for the 12-month tumor local control rate is greater than 84.0%.

PASS 12 was used to calculate the sample size needed. A sample size of 203 lesions achieves 85% power (and guarantees at least 80% power) to detect a difference ($P_1 - P_0$) of 0.0700 using a one-sided binomial test. The target significance level is 0.0250. The actual significance level achieved by this test is 0.0239. These results assume that the population proportion under the null hypothesis is 0.8400.

Power Analysis of One Proportion

Numeric Results for testing $H_0: P = P_0$ versus $H_1: P > P_0$

Test Statistic: Exact Test

Power	N	Proportion		Target Alpha	Actual Alpha	Beta	Reject H_0 If $R \geq$ This
		Given H_0 (P_0)	Given H_1 (P_1)				
0.8501	203	0.8400	0.9100	0.0250	0.0239	0.1499	181

To account for up-to a 10% 12-month lesion attrition rate, the final sample size has been increased to 226 lesions.

Note that, for the purposes for sample size calculations, the observations are assumed to be independent. However, the primary analyses will account for within subject correlation, as described below.

General Analysis Methods

Data will be analyzed using descriptive statistics. Continuous variables (e.g., age) will be summarized by the number of patients, mean, standard deviation, median, interquartile range, minimum and maximum. Categorical variables (e.g., race) will be summarized by frequencies and percentages of patients in each category. 95% confidence intervals will be calculated as appropriate.

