For the formal primary endpoint hypothesis test, patients with missing 12-month tumor evaluations will be imputed using multiple imputation (SAS PROC MI using FCS logistic regression and including tumor status at prior visits), except in the following case where previous visit evidence can be used to impute 12-month status:

- Subjects with local tumor failure at 6-months will be considered a local tumor failure at 12-months post-index procedure.

Additional sensitivity analyses to be conducted:

- Worst case: all missing data are imputed to be failures
- Best case: all missing data are imputed to be successes
- Complete case: all missing data are treated as missing and not imputed

Subset Analyses

Analysis will be done on outcomes for subgroups including, but not limited to, gender and lesion size. Additional non-protocol defined subgroups include: number of needles used, number of lesions, primary cancer diagnosis, and lesion location.

Poolability Analyses

A poolability analysis among investigational centers and geographies (US/OUS) will be performed for the primary efficacy endpoint. This analysis will be performed on the ITT population.

Poolability of Sites

Combining of Small Sites

Sites contributing less than 5 subjects to the as treated analysis set will be considered “small sites” and ordered by the date of first enrollment in the as treated analysis set. Starting with the first “small site”, a pseudo-site will be created by adding subjects from successive “small sites”. If the number of subjects reaches or exceeds the size of the median enrollment of the “large sites”, then a second pseudo-site will be created. Additional pseudo-sites, if needed, would be created in the same manner.

Primary Endpoint by Site

Among sites and pseudo-sites, the proportions of subjects who achieve local tumor control at 12 months will be compared using logistic regression. If the resulting p-value is ≤ 0.05 , further exploratory analysis will attempt to identify covariates (baseline characteristics) that may explain differences among the sites. Otherwise, the data will be considered to be poolable across study sites.

Poolability of Geographies

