4.0	Jan 4, 2017	
 • Study Design: Clarified enrollment targets - removed numbers not accounting for attrition. • Sample Size Justification: clarified rate being tested; defined C_{DEVICE}; removed ‘exact’ specification on CI as final endpoint test will be the random effects model. • Analysis Populations: clarified primary analysis will be on ITT using multiple imputation; expanded PP definition to include removal for major deviation; clarified missing data imputation and additional sensitivity analysis to be defined in another segment. • Efficacy Endpoint Analysis: removed “low number of multi-lesion subject” section as the study had >10 subjects with multiple lesions. • Supportive Endpoint Analyses: clarified wording on “weighted average response”. • Handling of missing data: added specific imputations for primary hypothesis test; added specific imputation methods for sensitivity analyses. • Subset Analyses: Added additional subgroups of interest • Poolability Analyses: Corrected population to ITT as this is the primary endpoint population; Added a test of pooling by geography (US/OUS); changed pooling significance level to 0.05 (instead of .15 usually done to account for interactions) as this is a one group study and only main effects will be tested. • Added more specific methods of analysis throughout.

Approvals

Name	Study Role	Signature	Date
[REDACTED]	Galil – [REDACTED]	DocuSigned by: [REDACTED]	04-Jan-2017
[REDACTED]	Galil – [REDACTED]	DocuSigned by: [REDACTED]	05-Jan-2017
[REDACTED]	NAMSA – [REDACTED]	DocuSigned by: [REDACTED]	05-Jan-2017
[REDACTED]	BTG – [REDACTED]	DocuSigned by: [REDACTED]	05-Jan-2017

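### The SAP's site poolability test names no test statistic and has no rule for sites without failures; if the Wald p-value is used at the planned site sizes, it declares the data poolable almost by default

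*SAP*

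**What the plan says.** The SAP, under Poolability Analyses (Primary Endpoint by Site), sets out the comparison in one sentence: "Among sites and pseudo-sites, the proportions of subjects who achieve local tumor control at 12 months will be compared using logistic regression". A p-value at or below 0.05 leads to an exploratory search for baseline covariates that might explain the differences. For every other result the SAP says "Otherwise, the data will be considered to be poolable across study sites". The revision history records that the threshold was lowered: "changed pooling significance level to 0.05 (instead of .15 usually done to account for interactions".

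The section names no test (Wald, likelihood ratio, score or exact) and does not mention sites in which every subject has local control. Only sites with fewer than 5 subjects are merged into pseudo-sites, so a site of 5 to 10 subjects stands alone.

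On size, Protocol section 5 expects "150 patients across approximately 15 study sites in the United States and internationally", and the SAP states "Target inclusion for this study is 226 lesions". Elsewhere the SAP does name Wald inference for logistic models: for the primary random effects model and for the supportive patient-level logistic regression.

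**The concern.** With about 10 patients per site and about 90% control, several sites will probably have no failures. In a logistic model with a site factor, the log-odds for such a site runs off to infinity while its information goes to zero. The site then adds nothing to the joint Wald chi-square but still uses a degree of freedom. The other sites have to exceed a critical value set for all of them.

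The candidate p-values from one fitted model can therefore disagree completely, and the SAP leaves the choice open. The trial has a single arm and is judged by one pooled rate against 84%. The site check is the planned look at whether that rate conceals centers with poor control. If the Wald p-value is used, non-rejection is close to automatic at the planned layout, yet it would be reported as evidence that the sites can be pooled.

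**Working it through.** **The plan's own figures.** The SAP gives no operating characteristics for the poolability test. Its primary sample size reproduces: with 203 tumors and rejection at 181 or more, the exact binomial gives alpha 0.0239 at 0.84 and power 0.8501 at 0.91, and 203/0.90 = 225.6, rounded up to 226.

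**Inputs from the documents.** 150 patients over about 15 sites, so about 10 per site. 226/150 = 1.5 tumors per patient. Control is 0.84 under the null ("These results assume that the population proportion under the null hypothesis is 0.8400") and 0.84 + 0.07 = 0.91 under the alternative. The poolability threshold is 0.05.

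**Assumptions.** Site sizes and the spread of site effects are not in the documents. Several layouts are shown.

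**Step 1: sites with no failures.** With 15 sites of 10, the expected number is 15 × (control rate)^10.
- 91%: 15 × 0.389 = 5.8
- 87% (a subject succeeds only if all tumors are controlled; 0.91^1.5 ≈ 0.87 under independence): 3.7
- 84%: 2.6

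The chance of at least two such sites is 99%, 92% and 77%.

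**Step 2: one data set by hand.** Take 15 sites of 10 with 18 failures: eight sites with 0, four with 1, and three with 4, 5 and 5. There are 14 degrees of freedom, and the 5% critical value is 23.68.
- Score (Pearson): each site expects 1.2 failures with variance 10 × 0.12 × 0.88 = 1.056. The squared deviations sum to 8(1.44) + 4(0.04) + 7.84 + 2(14.44) = 48.4. The statistic is 48.4/1.056 = 45.8, p = 0.00003.
- Likelihood ratio: p = 0.00009.
- Wald, in the limit: zero-failure sites have weight 0. The weights w = 10p(1−p) are 0.9 (four sites, log-odds −2.197), 2.4 (log-odds −0.405) and 2.5 (two sites, log-odds 0), summing to 11.0. The weighted mean is −0.808. The statistic is 3.6(4.828) + 2.4(0.164) − 11.0(0.652) = 10.6, p = 0.72.

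The same model and data lead to opposite poolability conclusions.

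**Step 3: rejection rates by simulation, 15 sites of 10, threshold 0.05.** Ranges are across separate runs. The estimate does not exist for a zero-failure site, so Wald results also depend slightly on where the iterations stop.

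| True control | Wald | Likelihood ratio | Score | Permutation |
|---|---|---|---|---|
| two sites 50%, rest 93% | 0.7–1.3% | 91–92% | 90% | 90% |
| three sites 60%, rest 95% | 0.2–0.4% | 91–92% | 89% | 89% |
| one site 60%, rest 90% | 0% | 36–37% | 31% | 30% |
| no difference, 88% | 0% | 8–9% | 4–5% | 4% |

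**Step 4: other layouts.**
- Two sites at 50% and the rest at 93%: Wald power is about 16% at 12 sites of 12, 56% at 10 of 15 and 88% at 8 of 19.
- Uneven sites of 5 to 30 patients: Wald 19% in one layout (two sites at 50%, rest at 95%; likelihood ratio 99.7%, permutation 99%) and 0–7% in another (likelihood ratio and score 69–97%).
- Random enrolment of 135 or 150 patients with the SAP's merging rule leaves about 12 units. With site effects of SD 1 on the logit scale, Wald rejects 1.7–8.1%, score 46–63% and likelihood ratio 52–70%. With SD 1.5, Wald rejects 10–25% and score 78–89%.

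**The case against.** The strongest objection is that the SAP never names Wald for this test. Its Wald wording concerns confidence intervals for control rates, not a comparison of many sites. Likelihood ratio and score p-values come from the same fit, satisfy the text in full, and have about 90% power in the cases above. This stands: a reader might infer that the test as written cannot detect even gross site differences, and the documents do not support that. They leave the statistic open.

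Second, near-zero Wald power belongs to many small sites. The protocol's 15 sites is an estimate, and Step 4 shows substantial recovery with fewer, larger ones. This also stands.

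Third, the count of zero-failure sites depends on the control rate. If a subject must have every tumor controlled and the tumor rate is only 84%, then 0.84^1.5 = 0.77 and 15 × 0.77^10 = 1.1 sites. That makes several such sites less certain, but it does not rescue the Wald test: with no site difference it still rejected 0% at 77 to 88% control.

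Fourth, a significant result triggers only exploratory covariate work. A reader might infer that pooling would otherwise be withheld or that the primary result is at risk. Neither follows, because the SAP runs the primary test the same way whatever this check shows.

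**Conclusion.** The concern holds as a specification gap with a material consequence under one permitted choice. The site p-value is undefined, there is no zero-failure rule, and the candidate tests range from about 1% to about 90% power at the planned layout. If Wald is used there, poolability is declared almost by default. The size rests on about 15 equal sites of 10, on 84 to 91% control, and on the assumed site differences. With fewer or larger sites the loss is partial, and at 8 sites of 19 it is small.

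The effect is confined to the poolability conclusion and its exploratory follow-up. The primary test is unchanged. The US versus non-US comparison is largely unaffected, since two large groups rarely have zero failures and Wald power there was similar to the other tests. The point merits a change to the SAP but is secondary to the primary analysis.

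**What to change.** State that the site p-value comes from an exact test (Fisher-Freeman-Halton, or a permutation of whole patients across sites) or from the score test of the planned logistic model, and not from the Wald test. With no site differences, the exact test rejected about 3–4% and the score test about 4–5%. The ordinary likelihood ratio test also detects differences but runs at about 6–10% under no difference, so it is second choice.

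State that the test uses observed subject-level outcomes. If multiply imputed outcomes are to be used, as in the primary analysis, give the rule for combining the p-values. Report each site's and pseudo-site's control rate with an exact interval, so that the conclusion does not rest on one p-value.

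The cost is a line or so of SAP wording and one different test, with no new data. The downside is that poolability may be rejected more often, which would bring the planned exploratory work into play.

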Analysis Populations

All primary analyses will be performed on all tumors with a Galil Medical Cryoablation System and needles as the intent-to-treat evaluable population. A supplemental per-protocol analysis

will be done for the primary endpoint, removing tumors that 1) did not have a complete treatment; and subjects who 2) did not meet the study criteria but were enrolled; or 3) had a deviation with high likelihood of affecting the study outcome (as determined by a review of all occurring deviations).

The intent-to-treat and per-protocol analyses will be compared for level of agreement. It is expected that the two populations will be similar; however, any substantial differences between the two will be analyzed appropriately to elucidate the cause of these differences. Missing data will be imputed for the primary analysis as outlined in section "Handling of Missing Data" section later in the SAP. Additional sensitivity analyses using alternate missing data imputation will be presented.

Efficacy Endpoint Analysis

Efficacy Endpoint

The primary efficacy endpoint for this study is assessment of cryoablation on local tumor control in patients with pulmonary metastatic disease at 12 months post cryoablation.

Analysis Methods

The primary efficacy endpoint for this study is defined as follows: local tumor control in patients with pulmonary metastatic disease at 12 months post cryoablation. Tumor control will be defined by the criteria defined in Section 9.7 of this protocol.

Patients are allowed up to 6 tumors and the primary efficacy endpoint (tumor control) will be calculated on a per tumor level.

The rate of local tumor control at 12-months will be analyzed using a random effects logistic regression model accounting for within subject correlation to account for multiple tumors per subject. The null hypothesis will be tested comparing the lower bound of the Wald 97.5% one-sided confidence interval for the estimated rate of local tumor control to the performance goal of 84.0%. If the lower bound is greater than 84.0%, the null hypothesis will be rejected and the endpoint will be considered met.

Safety Endpoint Analysis

Safety Endpoint

The safety endpoint for this study is to assess the incidence and severity of cryoablation related adverse events.

Analysis Methods

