Among geographies (US vs. OUS), the proportions of subjects who achieve local tumor control at 12 months will be compared using logistic regression. If the resulting p-value is ≤ 0.05 , further exploratory analysis will attempt to identify covariates (baseline characteristics) that may explain differences among the geographies. Otherwise, the data will be considered to be poolable across study geographies.

Interim Reporting

Interim reports may be prepared until the initial manuscript reporting the treatment results has been submitted. The usual components of this report are:

- a) patient accrual rate
- b) distribution of pre-treatment characteristics
- c) cryoablation procedure details
- d) frequency and severity of the toxicities

Statistical Software

All statistical analyses will be produced using SAS software Version 9.3 or above (SAS Institute, Cary, NC.).

Version, Revision History, and Approvals

Current Version

Version 3.3 – Approval Date: Dec 8, 2016

Revision History

Version	Approval Date	Key Changes
1.0	Jan 21, 2014	Initial Release
2.0	Feb 12, 2014	Updated to reflect changed to study protocol v2.
3.0	May 14, 2014	Corrected endpoint text to correctly reflect the study endpoint of “12-month tumor local control”.

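### The site and US/OUS poolability tests compare proportions of subjects, with no success rule for a subject with several tumours, although the primary endpoint they are meant to check is per tumour.

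*SAP*

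**What the plan says.** SAP, Poolability Analyses, opens with its purpose: "A poolability analysis among investigational centers and geographies (US/OUS) will be performed for the primary efficacy endpoint". On the population it says: "This analysis will be performed on the ITT population".

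That endpoint is defined in SAP, Efficacy Endpoint Analysis: "Patients are allowed up to 6 tumors and the primary efficacy endpoint (tumor control) will be calculated on a per tumor level". The 12-month control rate "will be analyzed using a random effects logistic regression model accounting for within subject correlation to account for multiple tumors per subject".

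The two poolability tests use another unit. Under Primary Endpoint by Site, the comparison (pseudo-sites included) reads: "the proportions of subjects who achieve local tumor control at 12 months will be compared using logistic regression". Poolability of Geographies repeats the same rule for US versus OUS. Neither test mentions a within-subject term. In each, a p-value of 0.05 or less starts an exploratory search for baseline covariates; otherwise the data are declared poolable.

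The poolability section gives no subject-level success rule. The only one in the SAP is under Supportive Endpoint Analyses, where a patient succeeds only if every lesion is controlled. Protocol 10.4 does not settle the unit. Protocol 10.5.3 requires each treated tumour to meet the control criteria, but within a paragraph that sets the endpoint per tumour.

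Under Combining of Small Sites, sites are counted and ordered using the "as treated analysis set". Neither document defines that set. The SAP defines only ITT evaluable and per-protocol populations, and its Subject Disposition list names only those two.

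**The concern.** A poolability test should examine the quantity that is being pooled. Here that is the tumour-level control rate, but the text compares subject-level proportions. How the two relate depends on a rule that the section does not give:

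- **All lesions controlled:** subject success falls as the number of lesions rises, even when every tumour has the same chance of control.
- **Any lesion controlled:** subject success rises with the number of lesions.
- **Subjects used loosely for tumours:** the unit is then right, but a plain logistic regression treats tumours in the same patient as independent, which the primary analysis deliberately does not do.

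Under the first two rules, a region or site that treats patients with more lesions can look different when its tumour control is the same. A real tumour-level difference can also be masked. Multi-lesion patients are expected: the plan has 226 tumours in 150 patients, and the SAP revision history records more than 10 subjects with multiple lesions.

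**Working it through.** **Plan's own figures.** The exact binomial design reproduces. With 203 tumours and rejection at 181 or more successes, alpha is 0.02388 at 84% (stated 0.0239) and power is 0.85008 at 91% (stated 0.8501). Inflation for attrition is 203 / 0.90 = 225.6, rounded up to 226. The design rate of 91% is used below.

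**Inputs from the documents.** Per-tumour control 91% (SAP, Sample Size Justification); up to 6 tumours per patient; 226 / 150 = 1.51 tumours per patient; about 15 sites (Protocol 5), so 150 / 15 = 10 patients per site; poolability threshold p ≤ 0.05.

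**Assumptions not in the documents.** Within-patient ICC from 0 to 0.5; lesions per patient distributed as 1 + Binomial(5, ·); 75 patients in each geography; equal site sizes.

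**Step 1: subject success under the all-lesions rule.** With independent tumours the probability is p^m. With beta-distributed patient probabilities, a = p(1 − ICC)/ICC and a + b = (1 − ICC)/ICC, so for m = 3 it is p × (a+1)/(a+b+1) × (a+2)/(a+b+2).

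- ICC 0: 0.91³ = 0.754.
- ICC 0.3: a = 2.123, a + b = 2.333, so 0.91 × 3.123/3.333 × 4.123/4.333 = 0.811.
- ICC 0.5: a = 0.91, a + b = 1, so 0.91 × 1.91/2 × 2.91/3 = 0.843.

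| Lesions | ICC 0 | ICC 0.3 | ICC 0.5 |
|---|---|---|---|
| 1 | 91.0% | 91.0% | 91.0% |
| 2 | 82.8% | 85.3% | 86.9% |
| 3 | 75.4% | 81.1% | 84.3% |

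**Step 2: false-signal rate.** Every tumour has 91% control and only lesion counts differ. The test is a likelihood-ratio logistic test on all-lesion success at p ≤ 0.05, with 8,000 simulated trials per scenario.

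| Comparison | Mean lesions | ICC 0 | ICC 0.3 |
|---|---|---|---|
| US vs OUS, 75 each | 1.51 vs 1.51 | 5.3% | 4.8% |
| US vs OUS, 75 each | 1.2 vs 1.81 | 13.8% | 9.2% |
| US vs OUS, 75 each | 1.0 vs 2.01 | 30.6% | 15.8% |
| 15 sites of 10 | 1.51 in all | 9.2% | 8.1% |
| 15 sites of 10 | 1.0 (8 sites) vs 2.09 (7 sites) | 18.8% | 11.9% |

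The site test exceeds 5% even with equal counts, so its excess should be read against 8–9%.

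**Step 3: masking.** If one group has 91% tumour control with two independent lesions per patient, its subject success is 0.91² = 82.8%. A group with one lesion per patient and 82.8% tumour control gives the same figure, so a tumour-level gap of 91.0 − 82.8 = 8.2 points disappears. This case is deliberately stark; it shows the direction, not an expected size.

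**Step 4: if subjects means tumours.** An ordinary tumour-level logistic test across 15 sites with equal lesion counts and no true difference gives p ≤ 0.05 in 23.4% of trials at ICC 0.3, against 8.9% at ICC 0. For US versus OUS the figures are 7.7% and 5.4%.

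**The case against.** **The all-lesions rule is imported.** A reader might infer that the SAP specifies an all-lesions test for poolability. It does not; that rule belongs to a supportive analysis. SAP, Handling of Missing Data, also refers to subjects when it describes tumour failure at 6 months, so loose wording is plausible here. This stands, and the lesion-count figures are conditional on the rule. The point survives because the unit is unclear and each reading has a fault.

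**Large gaps need extreme cases.** A gap of 91.0 − 75.4 = 15.6 points needs one group entirely of one-lesion patients, another entirely of three-lesion patients, and independent tumours. The plan averages 1.51 lesions, and its primary model allows for correlation. This stands too: the milder geography scenario (9–14%) is the more useful guide.

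**A false signal costs little.** It only starts an exploratory covariate search. The number of index tumours is recorded at baseline and the number of lesions is a listed subgroup, so the cause would probably be found. This is fair for false signals but gives no protection against masking, since a p-value above 0.05 leads directly to a declaration of poolability.

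**One outcome per subject avoids clustering.** That is a recognised approach, but it needs a stated success rule and still tests a different quantity from the primary endpoint.

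**The as-treated label is a leftover.** Protocol 10.3 defines ITT as all treated tumours, so the two sets may nearly coincide, and the SAP revision history shows that ITT was intended. This stands. A reader might infer that the label contributes to the lesion-count effect; it does not.

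**Conclusion.** The mismatch is real and minor. The section names a per-tumour endpoint, tests a subject-level proportion, and leaves subject success undefined. Under the all-lesions rule, the false-signal rate for US versus OUS is about 9–14% for a moderate imbalance in lesion counts and 16–30% for a strong one, against about 5% with none. These ranges run from ICC 0.3 to ICC 0 and rest on the assumed lesion distribution and equal geography split.

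A reader might infer that the primary result is at risk. The documents do not support that: the primary test is run on tumours with its own random effects model, and poolability neither gates nor changes it. The consequence is confined to the poolability conclusion and its exploratory follow-up.

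**What to change.** In SAP, Poolability Analyses, test geography, and site or pseudo-site, as terms in the tumour-level logistic model on ITT tumours, keeping the within-subject random effect. Simply replacing subjects by tumours in the present sentence is not enough, because the clustering would then be ignored. If a subject-level comparison is kept as a supplement, state its success rule.

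Separately, form small sites and pseudo-sites from subjects with ITT tumours instead of the undefined as-treated set.

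The cost is a wording change: no new data, and a model the SAP already specifies. The small downside is sparse failures. At 91% control, 226 × 0.09 is about 20 failures in all, and a site with about 15 tumours (226 / 15) has none with probability 0.91^15 = 24% if tumours are independent. Site effects may therefore be hard to estimate, so the SAP should say what is reported if the model does not converge. The planned test shares this sparsity, and the performance of the clustered site test was not evaluated here.
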